10.3. Method of determining the sample size

This is a post-authorization study. The size of the research group (n=500) was determined taking into account some practical limitations associated with the Study realisation and without the use of statistical sample selection tools. This should be taken into account when interpreting the study results.

10.4. Statistical analysis

Statistical analysis of the collected data will be carried out in accordance with the standards of the EU-GCP / ICH.

In general, all data will be summarized and presented using descriptive statistical methods. Appropriate statistical tests will be used for the analysis of the changes in assessed parameters, depending on the distribution of the variables and their type (continuous, categorized).

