STATISTICAL METHODS:	The sample size of 500 Patients was based on the feasibility study. The analysis of the data obtained in the Study will be descriptive: the compiled data will consist of summarizing statistics such as quantities, average values, standard deviations, medians, minimal and maximal values of the observed frequencies/proportions. The effectiveness analysis will be conducted on the basis of the population of Patients who will partake in all of the visits described in the Study Protocol.	

Table of contents

Study number: EUP/HED/008/2016 VERSION DATE: 21.11.2016

1. INT	RODUCTION	6
1.1.	Basic information on the subject affliction of this Study	6
1.2.	Information on the study drug	7
1.3.	The clinical reason for conducting this Observational Study	8
2. TH	E AIM OF THE STUDY	9
2.1.	The main aim of the Study	9
2.2.	The additional aim of the Study	9
3. STU	JDY DESIGN	10
3.1.	Basic information	10
3.1.	1. Characteristics of the study population	10
3.1.2	2. Study design	10
3.2.	Endpoints	10
3.3.	Substantiation of the study construction	10
3.4.	Duration of the Study	11
4. CO	MPLIANCE WITH TERMS OF GOOD CLINICAL PRACTICE, ETHICAL ISSUES.	11
5. STU	JDY POPULATION	11
5.1.	Records of the Study participants	11
5.2.	Inclusion criteria	12
5.3.	Exclusion criteria	12
5.4.	Procedures for treatment discontinuation or if the patient withdraws from the study	12
6. ME	THODOLOGY	12
6.1.	Schedule of the Study	12
6.2.	Assessments in a specialist and primary care clinics under the study	13
6.2.	1. Initial visit (Visit 1) - (day 0)	13
6.2.2		•
	the clinical needs of the Patient	
	SESSMENTS PERFORMED IN THE STUDY	
7.1.	Endpoints and the methods of their evaluation	
7.1. ⁻		
	JDY DRUG	
8.1.	Administration of the drug	
8.2.	Patient identification	
8.3.	Drug delivery	
8.4. 9. REI	Concomitant medication PORTING RELATED ADVERSE EFFECTS	
	TATISTICAL CONSIDERATIONS	
10. 5		
IU.I.	F QUEIL GIQSSIIIGAUUT ATU UEIITIUUT	10

DOCUMENT

STATUS: CONFIDENTIAL

10.2	2.	Analyses, populations, definitions	16
10.3	3.	Method of determining the sample size	17
10.4	1.	Statistical analysis	17
1	0.4.1	. Demographic data and other basic characteristics	17
1	0.4.2	2. Distribution of patients and cases of exclusion from the study	17
1	0.4.3	3. Adverse effects analysis	17
10.5	5.	Factors which may affect the statistical analysis and modify the results of the Study	18
10.6	6.	Factors limiting the Study	18
11.	M	ONITORING PROCEDURES	18
12.	MA	ANAGEMENT OF THE STUDY	18

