1.3. The clinical reason for conducting this Observational Study

HEDUSSIN[®] is a preparation containing dry extract of common ivy leaves as the active substance (825mg in 100 ml of the syrup) which is recommended in the treatment of wet cough of various aetiologies.

HEDUSSIN®, a medicinal product containing dry extract of common ivy leaves in the form of syrup, obtained the marketing authorisation (no. 22652) for medicinal products in Poland on 20.08.2015. Therefore the Study focusing on the assessment of the efficacy of the treatment in patients diagnosed with productive cough of various aetiologies is especially important to obtain data from the Polish population (the hitherto effectiveness findings were not obtained from the research on the Polish population). The data will be used for the purposes of planned marketing campaigns as well as staff, doctor and pharmacist trainings. The planned study of the HEDUSSIN® medicinal product can be carried out only on the trade name, as the subject of research interest is the specific medicinal product, administered in the form of syrup.

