2. THE AIM OF THE STUDY

2.1. The main aim of the Study

The assessment of the efficacy of the **HEDUSSIN**® medicinal product use in the treatment of productive (wet) cough evaluated on the basis of the severity and the treatment time of the infection occurring with a productive (wet) cough of various aetiologies in children aged 2-12.

The assessment of the efficacy of the **HEDUSSIN®** medicinal product will be based on:

- 1. Observation of the below symptoms and changes in their intensity during the treatment*:
 - The severity of the cough (from 0 to 4)
 - Dyspnoea (from 0 to 4)
 - Auscultatory changes (wheezing, dry rale, crackles) (from 0 to 4)
 - Chest pain during cough (from 0 to 4)
 - Hoarse breathing (from 0 to 4)

0- absent; 1- mild; 2- moderate; 3- severe; 4- very severe

- 2. Determination of the infection duration (measured in days)
- 3. Evaluation of the body temperature
- 4. The use of concomitant treatment:
 - The inclusion of an antibiotic
 - The inclusion of other medications and dietary supplements

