3.1.2. Study design

This project is an open-label, non-randomized, multicentre, non-interventional, post-authorization efficacy study (PAES).

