3.2. Endpoints

The gathering of information on the therapeutic effects of the treatment with the **HEDUSSIN®** medicinal product includes the assessment of: the number of days until full recovery of the Patient measured from the day of the 1st visit until the closure of the observation – the day of the 2nd visit.

- Exclusion from the Study the number of days measured from the day of the 1st visit until the occurrence of complications, intensification of the state, occurrence of additional infections, etc.

 visit 2: closure of the observation and the conducting of a medical interview on the health status/Patient wellbeing.
- The change in the intensity of the symptoms, associated with the respiratory system, resulting
 from the treatment will be assessed on the basis of the BSS scale (Bronchitis Severity Scale)
 (evaluation of the measurements taken during visit 1 and 2)
- The evaluation of the changes in the overall wellbeing resulting from the treatment will be based on the VAS scale (Visual Analog Scale) (evaluation of the measurements taken during visit 1 and 2)
- The evaluation of the treatment tolerance based on the occurrence of sleep quality disturbances and weakness feeling will take place on the basis of a 5-level estimation scale (evaluation of the measurements taken during visit 1 and 2)

All adverse effects caused by the drug must be reported to **Phytopharm Klęka S.A.** or the URPL or to the Study Organizer via the **www.dzialanianiepozadane.com** website.

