8.2. Patient identification

Throughout the duration of the Study all of the included patients must be identifiable. The investigator will maintain the list of the numbers of patients as well as their names and surnames, so that the records can be reached in the future, if necessary. The list of Patients participating in the Study should be kept confidentially at the study centre.

Patient number will be assigned during the first assessment in accordance with the chronological order of inclusion in the study in the resort. Patients in the course of this study will be identified using a unique identification number. Patient number and centre number will be recorded in the Study Questionnaire.

Patients qualified for the study are not covered by randomization.

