- Omission by the investigator to answer some of the questions included in the survey,
- The lack of information about the fate of the patient in the event of failure to report on the control visit

10.6. **Factors limiting the Study**

The limitations result from the duration of the observation (the length of the exposure) on the study drug.

The safety analysis will allow the assessment of the frequency of the adverse effects of the drug occurring in more than 1/1000 (very common, common and uncommon).

The obtained data will not permit a reliable assessment of the occurrence of rare and very rare adverse effects of the study drug which does not exclude the observation of drug adverse effects occurring with unknown frequency.

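### With one treated group and no comparator, section 3.2 attributes the Visit 1 to Visit 2 changes to the syrup and 10.4 adds tests of those changes, but the design cannot support that attribution

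*Protocol*

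**What the plan says.** - **Aim (2.1).** The main aim is "The assessment of the efficacy of the HEDUSSIN® medicinal product use in the treatment of productive (wet) cough evaluated on the basis of the severity"; infection duration is the other basis.
- **Design (3.1.2, 8.2).** The study is open-label and non-interventional, and "Patients qualified for the study are not covered by randomization". Under 5.2, only children already recommended the syrup are eligible. No control group, external reference or natural-course figure is given.
- **Endpoints (3.2).** For wellbeing: "The evaluation of the changes in the overall wellbeing resulting from the treatment will be based on the VAS scale". The BSS bullet attributes the symptom change to treatment in the same way. Both compare Visit 1 with Visit 2.
- **Analysis.** The summary says: "The analysis of the data obtained in the Study will be descriptive". Section 10.4 also puts descriptive methods first, but then adds: "Appropriate statistical tests will be used for the analysis of the changes in assessed parameters". The tests are to be chosen by the distribution and type of the variable.
- **Limitations.** Section 10.5 lists missed visits, stopping the drug, other drugs and unanswered questions as factors that may modify the results. Section 10.3 gives a caveat about sample size. Section 10.6 says: "The limitations result from the duration of the observation (the length of the exposure) on the study drug". It adds only what the study can and cannot say about adverse effects of given frequencies.
- **Use (1.3).** "The data will be used for the purposes of planned marketing campaigns", and for training of staff, doctors and pharmacists.

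**The concern.** A change between two visits in treated children mixes any drug effect with everything else that happens in 7-10 days. At least four other sources of change are present here:

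- natural recovery;
- regression to the mean, because children enter when their symptoms bring them to a doctor;
- antibiotics and other medicines, whose addition section 2.1 expects to be recorded;
- ratings recorded by the treating physician, who knows what was prescribed.

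Nothing in the design separates these from the syrup. Section 3.2 settles the question by wording: it defines the change as an effect of treatment before any data are seen. Section 10.4 then adds a p-value for a null hypothesis that does not concern the syrup.

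At stake is what the report may conclude. Someone who follows the protocol as written would credit the product with a change that the study cannot credit to it. Readers of the report would find nothing in the limitations section to warn them.

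**Working it through.** **What the tests can compare.** There is one group with two measurements and no reference value. Tests of the changes in the assessed parameters therefore take the form *mean (or median) change = 0*. A drug effect of zero does not make that hypothesis true.

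**Does the protocol itself expect change without a drug effect?** Section 1.1 describes the cough of viral upper respiratory infection as acute, lasting up to 4 weeks. Section 3.2 counts days to full recovery between the two visits. So improvement within the window is expected for at least part of the population. Its size is not given.

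**Inputs**
- n = 500 (10.3). This figure rests on feasibility, with no alpha, power, effect size or SD behind it, so there is no power calculation to reproduce.
- Two-sided 5% level: assumed, since the protocol states none.
- Drug effect: zero, by construction.
- Natural improvement d, in SDs of the change score: assumed, over the range 0.05 to 0.30.
- Children treated as independent, all 500 analysed: simplifying assumptions, varied below.

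**Formula** (paired test, normal approximation)

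P(significant) = Φ(d√n − 1.96) + Φ(−d√n − 1.96), with √500 = 22.36

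| d (SD) | d√n | d√n − 1.96 | P(significant), no drug effect |
|---|---|---|---|
| 0.05 | 1.118 | −0.842 | 20% |
| 0.10 | 2.236 | 0.276 | 61% |
| 0.20 | 4.472 | 2.512 | 99.4% |
| 0.30 | 6.708 | 4.748 | over 99.9% |

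The improvement that gives 99% is (1.960 + 2.326)/22.36 = 0.192 SD.

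**Sensitivity**
- Section 10.2 analyses only children with all assessments. With 250 completers (√250 = 15.81), d = 0.20 gives 88.5% and d = 0.30 gives 99.7%.
- With 500 children, 10 per physician and an assumed intraclass correlation of 0.20, the effective n is 500/(1 + 9 × 0.20) = 178.6. Then d = 0.20 gives 76% and d = 0.30 gives 98%.
- Section 5.1 also mentions a final group of 3000. At that size 99% is reached at 4.286/√3000 = 0.078 SD.

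**Would confidence intervals alone cure it?** No. A 95% interval for the mean change excludes zero exactly when the matching paired test has p < 0.05. Both inherit the same non-drug change, so only what is claimed from them can be corrected.

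**Do the limitations cover it?** Section 10.5 covers co-treatment and missed visits. No section names the missing comparator, natural recovery, regression to the mean or unblinded rating as a limit on interpretation.

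**The case against.** The strongest defence is that an uncontrolled non-interventional study is legitimate and openly declared here. The analysis is mainly descriptive by the summary and by the opening of 10.4. Section 2.1 already speaks of symptom changes over the course of treatment. Sections 10.3 and 10.5 carry caveats, and a statistical analysis plan may choose the tests. Much of this stands: the design is not an error, and the choice of test can be left to that plan. But an analysis plan does not rewrite the protocol's aim, its endpoint definitions or its limitations.

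A reader might infer more than the documents support:

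- **That a false finding of efficacy is near certain.** Section 10.4 sets no alpha, hypothesis or success criterion, and nowhere says that significance means efficacy. The probabilities above are chances of a significant change, not error rates of a stated decision rule. They are only 20% to 61% if natural improvement is 0.05 to 0.10 SD.
- **That the illness is self-limiting throughout.** The protocol does not say so. It admits cough of various causes, and section 1.1 names asthma and allergic rhinitis among the causes of chronic cough, where spontaneous improvement within 7-10 days is less sure.
- **That p-values will be marketed as proof.** Section 1.3 says that the data will be used in campaigns. It says nothing about p-values or proof.
- **That every endpoint is worded causally.** Only the BSS and VAS bullets attribute the change to treatment. The recovery-time and tolerance bullets do not.

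**Conclusion.** The point holds for three pieces of text: the attribution wording in 3.2, the mismatch between the descriptive analysis in the summary and the tests in 10.4, and the omissions from 10.6. Followed as written, the protocol attributes to the syrup a change that one uncontrolled group cannot attribute. That conclusion follows from the design and needs no numerical assumption.

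The figures show only how little a significant test would mean. With no drug effect, a natural improvement of about 0.2 SD or more makes significance very likely at n = 500, while 0.05 to 0.10 SD does not. The 5% level, the size of natural improvement and independence between children are assumptions that the protocol does not supply.

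**What to change.** 1. **3.2:** in the BSS and VAS bullets, replace the wording that makes the change a result of treatment with *during treatment*.
2. **2.1:** state that the study describes the change in symptoms and wellbeing, and the duration of the infection, during routine treatment.
3. **10.4:** align with the summary by making the change analysis descriptive, with an estimate and 95% confidence interval. State that neither a test nor an interval for change against zero is evidence of a drug effect.
4. **10.6:** add the missing comparator, natural recovery, regression to the mean, co-treatment and unblinded rating by the prescriber. State that the report will not attribute the change to the product.

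These are wording changes. Visits, questionnaires and sample size stay as they are. The cost is a weaker claim in the report and in the training and promotional material.

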10.4.1. Demographic data and other basic characteristics

Descriptive summary statistics (n, mean, standard deviation (SD), median, minimum, maximum) or frequency for demographic and basic characteristics data (medical history, co-morbidities, the primary disease diagnosis, previous treatment) will be presented.

10.4.2. Distribution of patients and cases of exclusion from the study

The number of patients treated, the number of patients who discontinued treatment with the study drug, and the number of patients who participated in the study visits will be presented in the form of tables. The main reasons for patients' discontinuation from participation in the study will be presented in the form of tables.

10.4.3. Adverse effects analysis

This Study is an efficacy assessment study (PAES) and its main aim is not focused on the research of the medicinal product safety – especially, the analysis of the reported adverse events will be conducted in a general manner as an auxiliary analysis in relation to the main aim of the Study, i.a. the efficacy assessment. The details on the safety of the used treatment contained within the Study Questionnaires will be included in the summaries of data on individual patients. Analysis and summary tables will be based on data from the study population taking into account the duration of exposure to the medicinal product under investigation.

All adverse effects will be coded in accordance with Medical Dictionary for Regulatory Activities (**MedDRA**).

The prevalence of all reported adverse effects and severe adverse effects occurring during the study will be presented in the form of tables.

In addition, summary tables will be presented, that will include data the maximum intensity of the adverse effect, the relationship to the study drug administration and related data on adverse effects as well as patients who discontinued treatment with the study drug due to the occurrence of adverse effects.

It is considered that related adverse effects occurring during the use of the study drug are any adverse effects that occur during an active study phase if:

They were not present prior to the first dose of study medication

or

• They were present prior to receiving the first dose of study drug, but its severity has been increasing during the observation.

All adverse effects occurring during the use of the study drug will be noted in the tables of adverse effects. Other medications used to treat concomitant diseases will be coded in accordance with the WHO Medication Coding Dictionary and will be summarized with the number and percentage of patients receiving concomitant medications and these patients will be grouped according to the pharmacological class of the medicine and International Non-proprietary Name (INN) of the drug.

10.5. Factors which may affect the statistical analysis and modify the results of the Study

- The Patients failure to report on the scheduled control visit
- The discontinuation of the study drug use for reasons other than adverse effects,
- Use other drugs during observation,

Study number: EUP/HED/008/2016

VERSION DATE: 21.11.2016

- Omission by the investigator to answer some of the questions included in the survey,
- The lack of information about the fate of the patient in the event of failure to report on the control visit

10.6. **Factors limiting the Study**

The limitations result from the duration of the observation (the length of the exposure) on the study drug.

The safety analysis will allow the assessment of the frequency of the adverse effects of the drug occurring in more than 1/1000 (very common, common and uncommon).

The obtained data will not permit a reliable assessment of the occurrence of rare and very rare adverse effects of the study drug which does not exclude the observation of drug adverse effects occurring with unknown frequency.

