6. METHODOLOGY

6.1. Schedule of the Study

A summary of observations and assessments that will be conducted during the study is presented in the following table.

Table1. Schedule of the assessments during the Study realisation

PROTOCOL FOR A NON-

INTERVENTIONAL

STUDY

Procedures for particular assessments	Visit 1*	Visit 2*
Demographic data	Х	
Qualification of the Patient into the PAES Study (inclusion criteria)	Х	
History concerning comorbidities and their treatments	Х	Х
Basic diagnosis and its duration	Х	
The dose of the medicinal product used		Х
The assessment of :		
 The symptoms associated with the respiratory system (BSS scale) 		
Assessment of the body temperature	Χ	Х
Assessment of the overall wellbeing (VAS scale)		
Assessment of the sleep quality disturbances		
The use of concomitant treatment		
Duration of the infection (number of days)		Х
Reporting adverse effects related to the HEDUSSIN ® medicinal product use		Х

^{*}The assessments will take place as part of the routine Patient observation

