9. REPORTING RELATED ADVERSE EFFECTS

If a related adverse event occurs, the Investigator is obliged to report each observed event by completing the DRUG RELATED ADVERSE EVENT REPORT and sending it in accordance with the Law on Medicinal Products to:

Phytopharm Kleka S.A. And

URPL

Study number: EUP/HED/008/2016

VERSION DATE: 21.11.2016

Should any severe adverse drug reaction occur, these should be reported within 24h.

The Investigator may additionally report the drug related adverse event to the Study Organizer through the **www.dzialanianiepozadane.com** website. The events reported to the Study Organizer via the abovementioned platform are forwarded to the URPL.

The addresses of all parties are available below:

Phytopharm Kleka SA, [name]

[name] and [name] (deputy) — Persons responsible for the pharmacotherapy safety on behalf of the Sponsor.

e-mail: [contact]

[contact]

Department for Monitoring of Adverse Action Medicines, Office for Registration of Medicinal Products, Medical Devices and Biocidal Products (URPL)

[name]

[name]

tel.: [name]

fax: [name]

e-mail: [contact]

Study Organizer Office: Europharma M.Rachtan Sp.z o.o.

[name]

Reporting via the platform: www.dzialanianiepozadane.com

The procedure for reporting ADR will be carried out in accordance with the standards of GVP

Reporting of adverse reactions associated with the use of the **HEDUSSIN**® medicinal product will be carried out in accordance with the provisions of the Pharmaceutical Law, in particular with art. 45 of the Act on professions of physicians and dentists.

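### Section 10.4.3 labels a timing-only rule as related, while section 9 and Table 1 require only drug-related events: the planned adverse-effect tables cannot all be correct

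*Protocol*

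**What the plan says.** **Definition.** Section 10.4.3 holds that "related adverse effects occurring during the use of the study drug are any adverse effects that occur during an active study phase", subject to one of two conditions. The first is new onset: "They were not present prior to the first dose of study medication". The second is that an effect already there at baseline has become more severe while the child was being followed. Both concern timing. Neither asks whether the drug caused the event.

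**Collection.** Section 9 sets the trigger for a report: "If a related adverse event occurs, the Investigator is obliged to report each observed event by completing the DRUG RELATED ADVERSE EVENT REPORT". Table 1 in section 6.1 schedules one safety item, at Visit 2: "Reporting adverse effects related to the HEDUSSIN ® medicinal product use". The Visit 2 list in section 6.2.2 does not repeat that item.

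**Planned output.** Section 10.4.3 states: "The prevalence of all reported adverse effects and severe adverse effects occurring during the study will be presented in the form of tables". It adds summary tables by maximum intensity and by relationship to the drug, and says that every adverse effect arising during use of the drug will appear in the tables. Section 10.6 then claims that the study can assess the frequency of effects occurring in more than 1 in 1000.

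**Recipients.** Section 3.2 allows a report to go to the sponsor "or the URPL or to the Study Organizer via the" website. Section 9 and the protocol summary require the sponsor and the URPL (the medicines authority), with the Study Organizer as an additional option.

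**The concern.** A treatment-emergent rule and a relatedness rule answer different questions. The first asks when an event began or worsened. The second asks whether the drug is suspected of causing it. Section 10.4.3 gives the first the name of the second.

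The distinction matters in this population. The children enrol with a respiratory infection and are observed for up to about 10 days, during which some may get worse for reasons unconnected with the syrup. The protocol expects this: section 3.2 provides for exclusion because of complications, intensification or additional infections. Dyspnoea shows the overlap. It is an efficacy item on the symptom scale in section 2.1 and also appears under allergic reactions in the adverse-effect list in section 1.2. By timing alone, worsening dyspnoea could be counted as drug-related.

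At stake are the adverse-reaction frequency that the study reports and the meaning of the relationship table. The recipient mismatch is a separate matter: it concerns who learns of an event more than how the event is tabulated.

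**Working it through.** The plan gives no figure to reproduce. The check is whether any one meaning of *related* makes definition, collection and tables agree.

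**Reading A: related means the timing rule of section 10.4.3.**
- Section 9 and Table 1 then cover every new or worsening event, so collection is wide enough for tables of all adverse effects.
- Every event tabulated as arising under the drug is related by definition. The relationship table has essentially one category.
- Events due to the infection count as drug-related, so that rate is overstated.

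**Reading B: related means a causal judgement**, as the title of the report form in section 9 suggests.
- The relationship label is meaningful.
- Nothing in section 9, Table 1 or section 6.2.2 requires an unrelated event to be recorded. The tables of all adverse effects are then incomplete, and the relationship table has no required source for an unrelated row.
- The definition in section 10.4.3 is wrong as written.

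Under A the relationship table fails; under B the tables of all effects do. The two failures belong to different readings and cannot be added together.

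**Sensitivity of the frequency claim.** Inputs: 500 planned patients (section 10.3) and the frequency bands in section 1.2 (uncommon from 1/1000 to below 1/100; common from 1/100 to below 1/10). With all 500 as denominator:
- one child counted: 1/500 = 0.2%, within the uncommon band;
- count at the common boundary: 500 × 1/100 = 5 children.

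So five children with the same symptom, counted under A and not under B, move that effect from unobserved to common. This shows how sensitive the result is. It does not estimate how many events would be reclassified.

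**Recipients.** Section 3.2 joins sponsor, URPL and organiser website with *or*. Section 9 and the summary join sponsor and URPL with *and*. Section 9 says that website reports are forwarded to the URPL and states no forwarding to the sponsor. A website-only report would satisfy section 3.2 but not section 9, and has no stated path to the sponsor.

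**The case against.** **Adverse effect may already mean drug reaction.** The summary, section 1.2 and section 3.2 use it that way. The timing rule would then only limit which suspected reactions count, and the relationship table could grade the strength of suspicion. This is the best defence, and the wording is ambiguous enough to allow it. It does not settle the matter: if adverse effect already implied causation, the qualifier *related* in Table 1 and section 10.4.3 would be redundant. On that reading the tables also show suspected reactions only, and should say so.

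**The questionnaire may hold more.** Section 3.3 says that it records tolerability, and section 10.4.3 refers to safety details in it. The form is not shown. This stands: related-only reporting is what the protocol requires, not proof of all that will be in the database. Likewise, the prevalence table is of *reported* effects, which related-only reports could literally fill. The later promise to tabulate all effects during drug use has no such limit.

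**Safety is auxiliary.** Section 10.4.3 says so, and this limits the weight of the point. Section 10.6 nevertheless makes a frequency claim that depends on what is counted.

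**The analysis plan could resolve it.** It could redefine terms, but it cannot recover events that nobody was asked to record.

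**Routing is editorial.** Largely so. Section 9 is the operative section and agrees with the summary.

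**Conclusion.** The point holds: the definition, the collection rule and the planned tables cannot all be correct together, and the frequency claim in section 10.6 depends on which reading is used. The protocol should be corrected, but the main efficacy aim is not affected.

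The documents do not support several stronger inferences that a reader might draw:
- *That every adverse-effect table will be wrong.* Which table fails depends on the reading, and the questionnaire may hold further data.
- *That every symptom of the infection will be counted as a drug effect.* This follows only if the timing rule governs and the investigator treats the symptom as an adverse effect.
- *That the error has a known size.* The protocol gives no rate of new or worsening symptoms and no expected share attributed to the drug. The arithmetic above shows sensitivity only, and assumes a denominator of 500.
- *That website reports go to the authority alone.* Section 9 states forwarding to the URPL and is silent on the sponsor. The organiser acts at the sponsor's request and may pass reports on.
- *That section 6.2.2 contradicts Table 1.* The list is incomplete, but Table 1 does schedule the item.

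**What to change.** 1. In section 10.4.3, rename the timing rule *treatment-emergent* and define *related* as the investigator's recorded causality judgement.
2. Choose one scope and apply it throughout:
   - record all adverse events with causality on the questionnaire at Visit 2, changing the Table 1 item and adding it to section 6.2.2; or
   - keep related-only collection, and restrict and retitle the tables as investigator-reported suspected drug reactions, without promising all adverse effects.
3. Word the frequency statement in section 10.6 to match the chosen scope.
4. Reconcile the recipient sentence in section 3.2 with section 9 and the summary, and state whether website reports are passed to the sponsor.

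Items 1, 3 and 4 are wording changes. The first option in item 2 adds one questionnaire block at an existing visit and a little data entry, with no diagnostic procedure. The second costs only wording, but gives up any description of unrelated events.
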